### 6.3.3 Dose Proportionality

The power model will be used to analyze the dose proportionality in  $AUC_{0-\text{last}}$ ,  $AUC_{0-\text{inf}}$  and  $C_{\text{max}}$  of HM15912. The estimate of  $\beta$  and the corresponding 90% CI will be derived.

The power model is defined as follows:

$$\log(PK_i) = \alpha + (\beta) * \log(\text{dose}_i) + \varepsilon_i$$

where  $PK_i$  is the PK parameter ( $AUC$  or  $C_{\text{max}}$ ) observation for the subject  $i$ .

$\alpha$  is the population intercept.

$\beta$  is the population slope.

$\text{dose}_i$  is the dosage(mg) for the subject  $i$ .

$\varepsilon_i$  is the random error;  $\varepsilon_i \sim N(0, \sigma^2_{\varepsilon})$  and independent.

The assumption for the Power Model is that the underlying relationship between log(PK parameter) and log(dose) is linear. The dose proportionality corresponds to the ratio of dose normalized geometric means ( $R_{\text{dnm}}$ ), which is defined as ratio of the predicted geometric mean of the highest dose relative to the predicted geometric mean of the lowest dose. The dose proportionality would be declared when the 90% CI for the  $R_{\text{dnm}}$  falls entirely within the limit of 0.8 to 1.25. Scatter plot of log(PK parameter) and log(dose) will be plotted with an estimated line.

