8.8. Pharmacokinetics Analyses

PK parameters will be summarized by using descriptive statistics, and concentration-time data will be summarized descriptively with tables and graphs by dose level (linear and log scale). The noncompartmental PK parameters listed in Section 3.2.2 will be calculated using R, SAS, or Phoenix® WinNonlin®.

Dose proportionality will be evaluated using the linear regression approach for the log-transformed PK parameters AUC_{0-t} , AUC_{inf} , C_{max} values and the log-transformed dose value. Graphical presentation of dose proportionality will also be provided. Additional analyses will be performed as deemed necessary upon review of the data as exploratory analyses.

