**Table 2: Randomization Numbers and Treatment Assignment**

Cohort	Randomization Numbers	Treatment Assignment	
1	101-108	0.05 mg/kg HM15912 (N = 6)	Placebo (N = 2)
2	201-208	0.1 mg/kg HM15912 (N = 6)	Placebo (N = 2)
3	301-308	0.5 mg/kg HM15912 (N = 6)	Placebo (N = 2)
4	401-408	1.0 mg/kg HM15912 (N = 6)	Placebo (N = 2)
5	501-508	1.5 mg/kg HM15912 (N = 6)	Placebo (N = 2)

Once a randomization number has been allocated to one subject, it may not be assigned to another subject. If subjects withdraw prematurely from the study and are replaced under the direction of the Sponsor, then a replacement randomization number will be assigned when a replaced subject has successfully completed screening. A replacement randomization code will be generated such that replacement subjects are assigned to the same treatment as the discontinued subjects. The replacement randomization code will differ only in randomization numbers. It is composed of 4 digits by adding "1" in front of the randomization number for a withdrawn subject. For example, if Subject 202 withdraws and is replaced, then the randomization number for the replacement subject will be 1202.

The study blind should not be broken except in a medical emergency (where knowledge of the IP administered would affect the treatment of the emergency), or if dose limiting toxicities occur or if it is necessary for dose escalation decisions. The decision to break the blind will be made by the Principal Investigator on a case-by-case basis. The Investigator or the Principal Investigator will contact Hanmi Pharmaceutical Co., Ltd. and deliver related documents when breaking the blind. The results of breaking the blind for each subject will not be revealed. The Investigator or the Principal Investigator will record blind-breaking dates and reasons in the CRF.

If blinding is not maintained in the Investigator, the institution's staff or subjects, the subject must be withdrawn. If blinding is accidentally broken during the study or blinding is broken before completion of the study due to SAEs, the Investigator must record this and rapidly report to Hanmi Pharmaceutical Co., Ltd. However, if blinding is broken for ethical reasons or blind breaking is seen to have little effect on the subject's safety, the subject may continue to participate in the clinical study in the judgement of the Investigator after discussing with Hanmi Pharmaceutical Co., Ltd.

After database lock, the overall randomization code will be broken.

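### SAP 6.3.3 defines the dose-proportionality ratio without dividing by dose, so the 0.8–1.25 rule as written tests for a slope near 0, not near 1

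*SAP*

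**What the plan says.** Protocol section 8.8 sets out the analysis only in outline: "Dose proportionality will be evaluated using the linear regression approach for the log-transformed PK parameters" (both AUCs and Cmax) on log dose. It gives no criterion.

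SAP section 6.3.3 fits log(PK) = α + β·log(dose) + error. The response is the subject's own AUC or Cmax, and the regressor "is the dosage(mg) for the subject". The slope is estimated "and the corresponding 90% CI will be derived", but no acceptance range for β is given.

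The decision rule rests on Rdnm. The SAP introduces it by name: "The dose proportionality corresponds to the ratio of dose normalized geometric means". It then states that Rdnm is "defined as ratio of the predicted geometric mean of the highest dose relative to the predicted geometric mean of the lowest dose". Proportionality is declared when the 90% CI for Rdnm "falls entirely within the limit of 0.8 to 1.25".

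SAP Table 2 plans six active subjects at each of 0.05, 0.1, 0.5, 1.0 and 1.5 mg/kg.

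**The concern.** The name and the definition of Rdnm describe different quantities. The fitted response is the raw PK parameter, so the predicted geometric mean is not dose-normalised, and taking its ratio between two doses does not make it so. For a proportional drug the undivided ratio equals the dose ratio, which is far from 1. Limits placed around 1 then accept a drug whose exposure does not rise with dose and reject one whose exposure rises in proportion.

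This is the only stated basis for declaring proportionality for AUC0-last, AUC0-inf and Cmax. A programmer who codes the definition and a second who codes the name would get different results, and the explicit wording supports the wrong one. If that is settled after the results are seen, a pre-specified rule has been changed post hoc.

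**Working it through.** The SAP gives no numerical result to reproduce here, so the check is algebra on its own model, followed by an illustration.

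**Inputs.** Power model, 90% confidence level and limits 0.8 to 1.25 (SAP 6.3.3); dose levels with six active subjects each (SAP Table 2). The documents give no between-subject CV for AUC or Cmax. Protocol 4.2 gives minimum body weights and a BMI range but no weight distribution. CVs and weight ranges below are therefore assumptions.

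**Step 1: the two ratios.** The predicted geometric mean at dose d is exp(α)·d^β. With r = highest dose / lowest dose:
- as written: [exp(α)·high^β] / [exp(α)·low^β] = r^β
- dose-normalised: r^β / r = r^(β−1)

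As planned, r = 1.5/0.05 = 30. At β = 1 the written ratio is 30, which is 30/1.25 = 24 times the upper limit; the dose-normalised ratio is 1. At β = 0 the written ratio is 1.

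**Step 2: what each rule requires of β.** Since 0.8 = 1/1.25, the 90% CI for β must lie within ±ln(1.25)/ln(r) of 0 (written) or of 1 (dose-normalised).

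| Highest dose studied (mg/kg) | r | ln(1.25)/ln(r) | Written rule: CI for β within | Dose-normalised rule: CI for β within |
|---|---|---|---|---|
| 1.5 | 30 | 0.0656 | ±0.066 | 0.934 to 1.066 |
| 1.0 | 20 | 0.0745 | ±0.074 | 0.926 to 1.074 |
| 0.5 | 10 | 0.0969 | ±0.097 | 0.903 to 1.097 |
| 0.1 | 2 | 0.3219 | ±0.322 | 0.678 to 1.322 |

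**Step 3: one fit, both formulas.** Take 30 active subjects, nominal doses and an estimated β of exactly 1. The sum of squares of ln(dose) is 52.08, t(28, 0.95) = 1.701 and σ = √ln(1 + CV²). The 90% half-width for β is 1.701·σ/√52.08. The interval is 30^(1 ± half-width) as written and 30^(± half-width) when dose-normalised.

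| Assumed CV | Half-width for β | 90% CI as written | 90% CI dose-normalised |
|---|---|---|---|
| 15% | 0.0352 | 26.6 to 33.8 (fail) | 0.887 to 1.127 (pass) |
| 20% | 0.0467 | 25.6 to 35.2 (fail) | 0.853 to 1.172 (pass) |
| 30% | 0.0692 | 23.7 to 38.0 (fail) | 0.790 to 1.265 (fail) |

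**Step 4: chance of a declaration.** Simulation with nominal doses, r = 30 and 400,000 draws per setting:

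| Assumed CV | Written rule, true β = 1 | Written rule, true β = 0 | Dose-normalised rule, true β = 1 |
|---|---|---|---|
| 10% | 0 | 0.997 | 0.997 |
| 15% | 0 | 0.854 | 0.853 |
| 20% | 0 | 0.510 | 0.508 |
| 25% | 0 | 0.197 | 0.198 |
| 30% | 0 | 0.046 | 0.045 |

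**Step 5: which doses define r.** The regressor is each subject's mg dose, which varies with body weight within a cohort, and the SAP does not say that highest and lowest refer to nominal levels. Separate simulations with mg doses (200,000 trials per setting, true β = 1) compared r = 30 with r taken from cohort geometric-mean mg doses. For weights of 45–85 kg the verdict differed in 2.1%, 3.5%, 3.1% and 1.3% of trials at CV 15, 20, 25 and 30%. The pass rate at CV 20% was 52.2% either way. Only the unlikely reading, the extreme individual mg doses, matters more: 9% to 18% of verdicts changed at CV 20% across assumed ranges from 55–75 kg to 45–85 kg.

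**The case against.** The strongest reply is that the sentence is elliptical. Its subject is the dose-normalised ratio, the rest says only which two doses are compared, and limits centred on 1 make sense only for that reading. The criterion also carries a citation to a published review of dose-proportionality methods. A literal implementation would show itself at once, with an interval of roughly 24 to 38 against limits of 0.8 to 1.25. β and its 90% CI are reported, so r^(β−1) can be recovered. No escalation rule and no sample-size argument uses the result.

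Much of this stands, and it limits the severity. The intent is hardly in doubt. A changed verdict also needs variability low enough for the intended rule to pass: with the estimate exactly at 1, both versions fail at CV 30%. For AUC0-inf, 30 subjects is a best case, because SAP 6.3.2 generally excludes subjects whose terminal slope is unreliable.

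It does not remove the point. The words that follow the name are an explicit definition, and they omit the division. Neither document states the formula or an acceptance range for β. The cited paper was not available for this review, and a decision rule should be readable from the SAP itself.

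**Conclusion.** The concern holds. As written, the rule would in practice never declare proportionality for a proportional drug: Rdnm would be near 30 when β is near 1, and a pass would need the 90% CI for β within ±0.066. These results follow from the SAP's model and planned doses alone. How often the slip would change the verdict depends on an assumed CV. The dose-normalised rule would pass in about 85% of trials at CV 15%, 51% at 20% and 4.5% at 30%, against none for the written rule.

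The consequence is confined to a secondary PK declaration, and a reader can recover the right answer from β. It should be fixed, but it does not threaten the study. The choice between nominal and mg doses for r is a minor clarification; nominal levels are the natural reading, since the PK output is organised by dose level.

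**What to change.** Before unblinding, replace the definition in SAP 6.3.3 with: Rdnm = (predicted geometric mean at the highest dose / highest dose) ÷ (predicted geometric mean at the lowest dose / lowest dose) = r^(β−1), with its 90% CI obtained by applying r^(β−1) to the limits of the 90% CI for β.

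State in the same place that r is the ratio of the highest to the lowest nominal dose level actually studied. As planned r = 30, so the rule is equivalent to the 90% CI for β lying within 0.934 to 1.066.

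Dose in mg can stay as the regressor. At any body weight w the two doses are 1.5w and 0.05w mg (90 mg and 3 mg at 60 kg), and their ratio is 30.

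The cost is one sentence in the SAP and at most one line of code, with no new data and no change to the model.

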## 6.4 Pharmacodynamic Analyses

### 6.4.1 Fasting Lipid Panel

The observed values and the change from baseline of fasting lipid panels, such as total cholesterol, triglycerides, LDL, HDL, VLDL, and FFA, will be summarized by treatment group, day and time point according to section 6.1.1.

### 6.4.2 Blood Glucose-related Panel

The observed values and the change from baseline of blood glucose panels, such as fasting plasma glucose, GIP, GLP-1, C-peptide, glucagon, and insulin will be summarized by treatment group, day and time point according to section 6.1.1.

### 6.4.3 Albumin and Pre-albumin

The observed values and the change from baseline of albumin and pre-albumin will be summarized by treatment group, day and time point according to section 6.1.1.

**6.4.4 Blood Plasma Citrulline**

The observed values and the change from baseline of blood plasma citrulline will be summarized by treatment group, day and time point according to section 6.1.1.

**6.4.5 Growth Factor**

The observed values and the change from baseline of insulin-like growth factor-1 and keratinocyte growth factor will be summarized by treatment group, day and time point according to section 6.1.1.

## 7. Interim Analysis

In the dose escalation meeting, blinded safety data collected at least 17 days post dose from at least 6 subjects (HM15912,  $n \geq 4$ ) in each cohort shall be reviewed prior to initiating the dosing of the next cohort. All pertinent blinded safety data, available PK and PD data, will be reviewed to make one of the following determinations:

- To continue with the study without modification.
- To continue with the study and add additional safety evaluations.
- To continue the study with adjustments made to the dose.
- Hold further enrollment pending evaluation / resolution of adverse events.

The dose escalation meeting will be held after at least the 6th subject completes the investigation of safety lab results at Day 17 in each Cohort. It is possible and acceptable that some queries may remain open and SDV will not be 100% for the applicable data. The level of SDV % will vary depending on factors such as monitoring schedule and availability of completed data entry and will not affect the dose escalation decision.

### 7.1 Dose Administration

- List of dose administration

### 7.2 Subject status

- Listing of Demographic data (including randomization numbers and cohort)
- List of completed subjects and early discontinued subjects with reasons

### 7.3 Adverse Events(AEs) and Serious AEs

- Listing of all AEs experienced, including reported terms, start/end date and time, severity, seriousness, relationship to study drug and outcome
- Highlight severity of “Moderate” or “Severe”
- Highlight relationship to study drug “Related”
- Identification of any AEs marked “Serious”
- Listing of dose administration

### 7.4 Clinical Laboratory Results

- Listing of all clinical laboratory tests, including hematology, clinical chemistry, coagulation and urinalysis according to SAP section 6.1.1
- Graphs of all laboratory results, including High/Low indicators
- Listings of abnormal laboratory values (with CS or NCS)

**7.5 12-lead ECG**

- List of all ECG results
- Graphs of all ECG results
- Listing of abnormal ECG findings (with CS or NCS)

**7.6 Vital Signs**

- List of all body weight, systolic/diastolic blood pressure, pulse rate, tympanic body temperature and respiratory rate assessments
- Graphs of vital sign assessments

**7.7 Abnormal Physical Examination Results**

- Listing of all PEs performed, not assessed as Normal, ordered by clinical relevance and body system

**7.8 Injection Site Reaction**

- Listing of all positive site reactions with diameter

**7.9 Concomitant Medication**

- Listing of prior concomitant medications that start before the date of dosing of study medication and continue beyond that date
- Listing of new concomitant medications that start after the first study dose date, including those started in the follow-up period

**7.10 Medical History**

- Listing of medical history by subject, description of the disease/procedure, MedDRA SOC, PT, start date and stop date (or ongoing if applicable)

**7.11 Pharmacodynamic (PD) Assessments (if available)**

- Graphs of all laboratory results, including High/Low indicators
- Listings of abnormal laboratory values (with CS or NCS)

**7.12 Pharmacokinetic (PK) Assessments (if available)**

- Graph of PK concentration
- Listing of PK concentration data
- Table of PK parameter with summary value

## 8. Statistical Software

All statistical analyses will be performed using SAS® version 9.4. All PK and PD parameters will be derived with standard NCA methods using SAS® version 9.4 or higher.

**10. APPENDIX****Table 3 Schedule of Assessments****Table 3-1. Schedule of Assessments (Cohort 1-3)**

Visit	Visit 1 Screening	Visit 2 Inpatient Treatment Period							Visit 3 Outpatient a	Visit 4 Outpatient a	Visit 5 Follow-up b		
		-1 Outpat- ient	-1 Inpa- tient	1	2	3	4	5	6	7			
Day	-28 ~ -2										10 (±1 day)	17 (±1 day)	30 (±3 days)
Informed consent	X												
Inclusion/exclusion criteria	X	X c											
Demographic data	X												
Height d , BMI e	X	X								X	X	X	X
Body weight d	X	X								X	X	X	X
Medical history	X	X f											
Prior/concomitant medications	X	X		X	X	X	X	X	X	X	X	X	X
Pregnancy test (all females) g	X	X											X
Serum FSH (postmenopausal females only)	X												
Urine drugs of abuse and alcohol screening	X	X								X	X	X	X
Viral serology	X												
Check-in			X										
Check-out									X				
Outpatient	X	X								X	X	X	X
Randomization		X											
Standardized meals			X	X h	X	X	X	X	X				

Visit	Visit 1 Screening	Visit 2 Inpatient Treatment Period									Visit 3 Outpatient a	Visit 4 Outpatient a	Visit 5 Follow-up b
		-1 Outpatient	-1 Inpatient	1	2	3	4	5	6	7			
Day	-28 ~ -2										10 (±1 day)	17 (±1 day)	30 (±3 days)
IP administration h				X									
Adverse event assessments	X	X	X	X	X	X	X	X	X	X	X	X	X
Vital signs (BP, pulse, tympanic temperature, RR) i	X	X		X i	X	X	X	X					
Clinical laboratory tests (hematology, chemistry, coagulation, urinalysis) j	X	X		X k		X k	X k			X		X	X
12-lead ECG l	X	X		X l	X	X	X			X	X	X	X
Immune response assessments (ADA, NAb, anti-PEG)				X m							X		X
Injection site assessments n					X	X	X	X	X	X			
Physical examinations	X	X		X	X	X	X	X	X	X	X	X	X
				■	■	■	■	■	■	■		■	■
Citrulline p				X	X	X	X	X	X	X	X	X	X
GIP, GLP-1, C-peptide, glucagon, insulin q				X			X			X		X	X
IGF-1 and KGF r				X			X			X		X	X

ADA = anti-drug antibody; Anti-PEG = anti-polyethylene glycol; BMI = body mass index; BP = blood pressure; ECG = electrocardiogram; FFA = free fatty acid; FPG = fasting plasma glucose; FSH = follicle-stimulating hormone; GIP = gastric inhibitory polypeptide; GLP-1 = glucagon-like peptide-1; HDL = high-density lipoprotein; IP = investigational product; LDL = low-density lipoprotein; NAb = neutralizing antibody; PK = pharmacokinetics; RR = respiratory rate; SC = subcutaneous; VLDL = very low-density lipoprotein

- a. An additional Outpatient visit may be included in later cohorts, if required, after PK data are evaluated. If so, assessments scheduled on Day 17 will be performed at the additional Outpatient visit.
- b. If a subject is discontinued from the study or withdraws consent, the Principal Investigator must make every possible effort to perform the evaluations described for the Follow-up visit. Efforts will be made to perform the Follow-up visit within 30 days from the date the subject is discontinued from the study or withdraws consent.
- c. The criteria applicable for admission prior to randomization, i.e., exclusion criteria 1, 2, 3, 5, 6, 7, 8, 9, 10, 11, 13, 14, 15, 16, 17, 19, 20, 21, 22, 24, 25, 27, 28, 29, 30, and 31, will be checked again.

- d. Height will be measured only at the Screening visit. Height and weight measurements will be performed with shoes removed. Weight will be recorded rounded to 1 decimal place. If weight is measured rounded to 2 decimal places, the number is rounded off from the second digit after the decimal point.
- e. BMI will be calculated by the following formula:  $BMI = \text{Weight (kg)} \div ((\text{Height (m)} \times \text{Height (m)})$ ). The calculated BMI will be rounded to 1 decimal place. The height measured at the Screening visit will be used for BMI calculation, and if a value is calculated as 2 decimal places, the number is rounded off to the first place.
- f. Medical history which will be checked on Day-1 is limited to the medical history related to exclusion criteria 1, 2, 3, 6, 8, 9, 10, 11, 13, 14, 15, and 17.
- g. Serum pregnancy tests at the Screening visit and on Day-1; urine pregnancy tests at the Day 30/Follow-up visit.
- h. HM15912 or placebo will be administered via SC injection into the abdomen on the morning of Day 1 after a minimum 10-hour fast. Subjects will continue fasting through approximately 4 hours postdose. Water consumption will also be limited for 1 hour before dosing and for approximately 2 hours after dosing. After the planned 4-hour post-dose blood sampling (clinical laboratory tests and analysis of citrulline) and testing (12-lead ECG) are performed, subjects will be served lunch by the institution.
- i. Vital signs will be measured twice per day on Day 1 through Day 6 (AM and PM). Vital signs will be measured at predose and 6 hours postdose on Day 1. Vital signs will be measured whenever possible in the morning and afternoon between Day 2 and Day 6. All other assessments will be performed once per day whenever possible. BP and pulse will be measured for 2 consecutive times after a subject has been lying down or sitting to rest  $\geq 5$  minutes, and mean values will be recorded.
- j. Samples for clinical laboratory tests will be collected after at least 12 hours of fasting. If the PK sampling time points are changed, the sampling times for clinical laboratory tests may be adjusted accordingly.
- k. 4, 48 and 72 hours postdose
- l. The 12-lead ECGs will be performed after a subject has been resting supine for  $\geq 5$  minutes. ECGs will be measured in triplicate in the morning during admission. Only for Day 1, however, ECGs will be measured in triplicate predose and 4 hours postdose, and a  $\pm 30$ -minute sampling window is allowed for measurement at 4 hours postdose. Triplicate ECGs will be recorded at least 30 seconds apart from each other, not exceeding a time period of 3 minutes for the completion of all 3 ECGs. 12-lead ECGs during the Outpatient visit will be measured once per day whenever possible.
- m. Blood sampling for immunogenicity assessments will be performed only for hospitalized patients after admission on Day-1, Day 10, and Day 30.
- n. Injection site assessments will be performed predose, within 1 hour postdose and at 4 and 12 hours postdose on Day 1, and then between 9:00 AM and 12:00 PM daily from Day 2 through Day 7.
- o. [REDACTED]

See Table 2-1 for the PK sampling schedule.

- p. If the PK sampling time points are changed, the citrulline sampling times may be adjusted accordingly. See Table 4-1 for the citrulline sampling schedule.

- q. Blood will be collected for GIP, GLP-1, C-peptide, glucagon and insulin immediately before administration and once daily on Days 4 and 7, at the Day 17 Outpatient visit and at the Day 30/Follow-up visit. If the PK sampling time points are changed, sampling times may be adjusted accordingly.
- r. Blood will be collected for IGF-1 and KGF immediately before administration and once daily on Days 4 and 7, at the Day 17 Outpatient visit and at the Day 30/Follow-up visit. If the PK sampling time points are changed, sampling times may be adjusted accordingly.

